### 10.6.3 Primary Efficacy Analysis

The primary efficacy variable (change from baseline in ETDRS BCVA letters to Week 12) will be summarized using continuous summary statistics, including 70%, 90% and 95% confidence intervals (CIs) for each treatment group. The primary analysis of the primary variable will employ a linear model with change from baseline ETDRS BCVA letters as the response, baseline ETDRS BCVA letters as a covariate, and treatment as a main effect factor, using the ITT population and with multiple imputation pattern mixture model techniques used to impute missing data. Subjects who receive rescue medication prior to Week 12 will have their Week 12 measure replaced with

their last observation prior to receiving rescue medication. The least squared mean, standard error, and CI for each treatment group, and the difference between treatment groups, will be presented as well as a 1-sided p-value testing the difference versus the null hypothesis value of 0. The study will be considered a success and DexNP superior to Vehicle if the one-sided p-value is less than 0.15 and the difference in mean change from baseline ETDRS BCVA letters is greater than 0. Analyses will secondarily be completed using a two-sample t-test.

The primary efficacy analyses will secondarily be performed on the ITT population using observed data only (ODO), last observation carried forward (LOCF), and baseline observation carried forward (BOCF) to assess the robustness of the results from the primary model. The primary efficacy analyses using multiple imputation and ODO will also secondarily be completed on the PP population. In all of these analyses, subjects who receive rescue medication prior to Week 12 will have their Week 12 measure replaced with their last observation prior to receiving rescue medication.

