## SYNOPSIS

Protocol Title:	Efficacy and safety of dexamethasone nanoparticles eye drops in diabetic macular edema.
Protocol Number:	DX211
EudraCT Number	2017-001172-36
Principal Investigator	[name]
Investigational Product:	Eye drops, DexNP 15 mg/mL, suspension Eye drops, Vehicle, suspension
Study Phase:	Phase IIb
Primary Objective(s):	The objective of this study is to evaluate the efficacy and safety of DexNP in the improvement of visual acuity in subjects with DME.
Secondary Objective(s):	Safety Morphologic changes Quality of Life
Endpoints:	Primary endpoint of the study is mean change in ETDRS BCVA letters at Week 12 compared to baseline.  Secondary endpoints of the study are number of patients with BCVA improvements of $\geq 10$ or 15 letters versus baseline, patients reaching 20/20 vision, central macular thickness on OCT, intraocular pressure, patient satisfaction.
Overall Study Design:	
Structure:	Multi-center, double-masked, randomized, vehicle controlled, prospective, parallel CT
Duration:	Maximum of 4 weeks of screening period, 12 weeks treatment until primary endpoint. Follow up without treatment for 4 weeks, total active study duration: 16 weeks.
Controls:	Vehicle.
Dosage/Dose Regimen/ Instillation/Application/Use:	Self-administrations. 1 drop into the study eye three times a day (8 hourly) for 12 weeks. Randomization is 2:1 (DexNP eye drops vs. Vehicle eye drops)
Summary of Visit Schedule:	Study visit schedule 

• Screening Visit (Day -1 to -28)

• Baseline (Day 1)

• Week 2

• Week 4

• Week 8

• Week 12 - Endpoint assessment

	

• Week 16 - final visit Visit window is <math>\pm</math> 3 days

Measures Taken to Reduce Bias:	Randomization will be used to avoid bias in the assignment of subjects to treatment, to increase the likelihood that known and unknown subject attributes (e.g., demographics and baseline characteristics) are evenly balanced across treatment groups, and to enhance the validity of statistical comparisons across treatment groups. Double-masked treatment will be used to reduce potential of bias during data collection and evaluation of clinical endpoints
Study Population Characteristics:	
Number of Subjects:	96

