### **10.3 Sample Size**

Assuming a difference in the mean change from baseline ETDRS BCVA to Week 12 of 3.5 letters between DexNP and vehicle, a common standard deviation in the change from baseline ETDRS BCVA letters to Week 12 of 8 letters within each treatment group, an overall 1-sided alpha = 0.15, a 2:1 randomization, and an interim analysis when 50% of the subjects complete Week 12 using an O'Brien-Fleming alpha spending function, 58 DexNP and 29 Vehicle subjects (study eyes) are required to have 80% power to reject the null hypothesis. Assuming 10% discontinuation rate, a total of 96 subjects will be randomized.

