### **10.4 Interim Analysis**

An interim analysis will be conducted by an independent biostatistician (to avoid introducing an operational bias) when approximately 50% of the subjects (44 subjects) complete Week 12. Statistical inference at the interim will be made at a 1-sided alpha = 0.04177. Statistical inference at the final analysis will be made at a 1-sided alpha = 0.13793. While there is no plan to stop early for a claim of superiority the O'Brien-Fleming boundary will serve to mitigate any concerns about that possibility and impacts overall power only minimally. If the interim is completed when precisely 50% of the subjects complete the trial through Week 12, the hypotheses will be tested using an efficacy boundary of 1.73051, corresponding to a one-sided alpha of 0.04177 at the interim analysis and using an efficacy boundary of 1.08968, corresponding to a one-sided alpha of 0.13793 at the final analysis. Note the actual boundaries will be calculated based on the percent of information used in the interim analyses.

No other study personnel other than the designated unmasked statistician and SAS programmers will be unmasked to the individual subject treatment assignments at the interim analysis. Additionally, a person appointed by the sponsor will be unmasked to treatment group summaries.

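### The primary linear model uses one residual variance under 2:1 allocation, so its standard error, interval and p-value hold only if both arms have equal spread; a robust or arm-specific variance should be prespecified.

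*Combined protocol and SAP*

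**What the plan says.** Section 10.6.3 defines the only success test. "The primary analysis of the primary variable will employ a linear model with change from baseline ETDRS BCVA letters as the response", with baseline BCVA as covariate and treatment as factor, in the ITT population after multiple imputation. A least-squares mean, standard error and interval are reported for each arm and for the difference, with a one-sided p-value. Nothing is said about how the variance is estimated.

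The same section adds: "Analyses will secondarily be completed using a two-sample t-test". It does not say whether that test is the pooled or the Welch form.

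Section 10.3 plans on "a common standard deviation in the change from baseline ETDRS BCVA letters to Week 12 of 8 letters within each treatment group" and "an overall 1-sided alpha = 0.15". The Synopsis and Section 4 give 2:1 allocation in favour of DexNP.

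Section 10.4 tests the final analysis "using an efficacy boundary of 1.08968, corresponding to a one-sided alpha of 0.13793 at the final analysis". Section 10.6.3 instead declares success "if the one-sided p-value is less than 0.15". That mismatch is a separate matter. The check below uses 0.13793, the level that Section 10.4 sets for the final test.

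**The concern.** A linear model with one residual variance pools the spread of both arms. With equal arms that matters little. With 58 DexNP and 29 vehicle subjects, the pooled variance is weighted about two to one toward DexNP, whereas the true variance of the treatment difference is weighted two to one toward vehicle. The weights are reversed, so unequal spread biases the standard error. It is too small if vehicle is wider and too large if DexNP is wider.

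The other analyses in 10.6.3 (observed data, LOCF, BOCF, per-protocol) vary the handling of missing data or the population. The Wilcoxon tests in 10.6.4 appear in the text on the VFQ-25. None of these addresses unequal variance in the primary model. At stake are the error rate of the success test and the coverage of the reported interval.

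**Working it through.** **Inputs from the plan.** Difference 3.5 letters, SD 8 in each arm, 58 and 29 evaluable, overall one-sided alpha 0.15, one O'Brien-Fleming look at 50% (10.3). Boundaries 1.73051 and 1.08968 (10.4).

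**Assumption.** The documents give no arm-specific SD of change. I used arm SDs with a pooled SD of about 8 and vehicle/DexNP ratios from about 0.62 to 1.7.

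**Step 1: reproduce the plan.**
- Spending at half information: 2[1 − Φ(1.4395/√0.5)] = 0.04177, as stated.
- Solving for an overall 0.15 gives a final boundary of 1.0897, as stated. The two stated boundaries together spend 0.1500.
- SE = 8 × √(1/58 + 1/29) = 8 × √0.05172 = 1.819. Standardised effect = 3.5/1.819 = 1.924.
- Group-sequential power is 80.6%, against 80% stated.

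The sample size is therefore consistent with its own inputs under equal SDs.

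**Step 2: the two variances.**
- Model: SE²(model) = s²(1/58 + 1/29), with s² = (57·SD_D² + 28·SD_V²)/85. Weight on DexNP: 57/85 = 67%.
- True: SE²(true) = SD_D²/58 + SD_V²/29. Weight on vehicle: two-thirds.
- Large-sample size of the final test alone: 1 − Φ(1.08968 × SE(model)/SE(true)).

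Worked case, DexNP 6.8 and vehicle 10:
- s² = (57 × 46.24 + 28 × 100)/85 = 63.95, so SE(model) = √(63.95 × 0.05172) = 1.819.
- SE(true) = √(46.24/58 + 100/29) = √4.2455 = 2.060.
- Size = 1 − Φ(1.08968 × 0.8827) = 1 − Φ(0.962) = 16.8%.

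**Step 3: the range.** The simulated column is the baseline-adjusted model on complete normal data.

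| SD DexNP / vehicle | Ratio V/D | SE model | SE true | Size, formula | Size, simulated |
|---|---|---|---|---|---|
| 8.0 / 8.0 | 1.00 | 1.819 | 1.819 | 13.8% | 13.8% |
| 7.2 / 9.4 | 1.31 | 1.818 | 1.985 | 15.9% | 15.7% |
| 6.8 / 10.0 | 1.47 | 1.819 | 2.060 | 16.8% | 16.8% |
| 6.2 / 10.8 | 1.74 | 1.822 | 2.164 | 17.9% | 17.9% |
| 8.6 / 6.6 | 0.77 | 1.819 | 1.667 | 11.7% | 11.7% |
| 9.0 / 5.6 | 0.62 | 1.829 | 1.574 | 10.3% | 10.4% |

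With an HC3 standard error the simulated size is 13.2% to 13.6% throughout. In the three wider-vehicle cases, coverage of the model's 95% interval is 92.8%, 91.8% and 90.3%, against 95.0% to 95.1% with HC3.

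**Step 4: power at 3.5 letters (simulated, final test).**
- Equal SDs: 79.4% for the model as written and 78.8% with HC3. Across runs the gap was 0.4 to 0.8 points.
- DexNP wider: 80.5% to 82.9% as written, against 82.7% to 86.4% with HC3. About 2 to 4 points are lost relative to the robust standard error, but power stays above the planned 80%.
- Vehicle wider: HC3 shows about 3 to 7 points less power than the model as written, because the inflated error rate has been corrected.

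**Limits.** The simulations omit multiple imputation, the rescue replacement and the interim look.

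**The case against.** The strongest objection concerns the null hypothesis. If DexNP does nothing at all, both arms have the same distribution, spreads are equal and the test has its nominal size. Inflation needs a drug with no mean effect that still changes the spread. That stands, and it limits the type I error argument. It does not protect the standard error and interval when the drug does have an effect, and spreads may then differ.

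The model is also a standard prespecified analysis, and the plan reports SDs and 70%, 90% and 95% intervals by arm. Unequal spread would therefore be visible. But it would be seen only after unmasking, when a change of variance method would be driven by the data.

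Four stronger readings are tempting, and the documents do not support them.
- *The earlier trial shows a wider control arm.* In the randomised trial against triamcinolone described in Section 1, follow-up logMAR SDs were 0.25 (DexNP) and 0.29 at 4 weeks, and 0.26 (DexNP, 8 weeks) and 0.37 (comparator, 12 weeks). The comparator was an active injection. The arms had 12 and 10 eyes, the SDs are of levels rather than change, and the last pair mixes visits. DexNP was the wider arm for baseline logMAR (0.30 against 0.28) and for macular thickness at baseline (141 against 94) and at 4 weeks (142 against 120).
- *Rescue will widen vehicle and inflate the error.* Carrying pre-rescue values to Week 12 could add a lower tail to the arm rescued more. More rescue on vehicle, though, mostly describes the alternative. If the drug has no effect, rescue should be alike in both arms.
- *The t-test pools.* Its form is not stated.
- *A wider DexNP arm leaves the trial underpowered.* In the cases examined, with pooled SD held near 8, power stays above plan.

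**Conclusion.** The point holds conditionally. The primary standard error, interval and p-value rest on equal spread, which Section 10.3 assumes and no listed analysis relaxes. Whether spreads will differ, and in which direction, cannot be settled from the documents. Nor do they show that the trial's error rate will exceed its declared level.

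Over the assumed range, the size of the final test moves from 13.8% to about 15.7–18% if vehicle is wider, and to about 11.7–10.4% if DexNP is wider. These figures assume normal complete data, 58/29 subjects and a pooled SD near 8. The change is a cheap improvement to the only success test. It does not repair a contradiction, and the planned analysis can be run as it stands.

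**What to change.** In 10.6.3, keep the linear model and its treatment estimate. Add that the standard error, confidence interval and one-sided p-value use a heteroscedasticity-robust (HC2 or HC3) or arm-specific variance within each imputed dataset, combined by the usual multiple-imputation rules. State that the secondary two-sample t-test is Welch's. Use the same variance method for the continuous BCVA and macular thickness models in 10.6.4. Settle this before any unmasking, including the interim.

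The cost is a few words of text and a software option. If spreads are equal, about 0.4 to 0.8 power points are lost at the final analysis. At the interim, with an assumed split of about 29/15, HC3 is slightly conservative: about 3.7% to 4.0% against the nominal 4.18%. If vehicle is truly wider, apparent power falls by the 3 to 7 points shown above.

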## **3 CLINICAL HYPOTHESES**

1. Proprietary DexNP eye drops improve visual acuity and decrease central macular thickness significantly more than vehicle in patients with DME.
2. Proprietary DexNP eye drop formulation is safe and well tolerated.

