### 5.3 Inclusion Criteria

**Each subject must:**

- a) Have DME of less than 3 years duration since diagnosis with presence of intraretinal and/or subretinal fluid in the study eye, with central

- macular thickness, CMT, of  $\geq 310\mu\text{m}$  by SD-OCT at baseline (Visit 2) (as measured by the Investigator).
- b) Have definite retinal thickening in the study eye due to DME involving the central macula based on the Investigator's clinical evaluation and by SD-OCT; Note: If the DME consists of circumscribed, focal leakage that the evaluating Investigator believes should be treated with laser and no other treatments, the eye is not eligible to be a study eye.
  - c) Have an ETDRS BCVA letter score  $\leq 73$  (Snellen 20/40) and  $\geq 24$  (Snellen 20/320) in the study eye at baseline (Visit 2)
  - d) Have a documented diagnosis of type 1 or type 2 diabetes mellitus and a glycosylated hemoglobin A1c (HbA1c) of  $\leq 12.0\%$  at Visit 1
  - e) Have a negative urine pregnancy test at Visit 1, if female of childbearing potential those who have experienced menarche and who are not surgically sterilized [bilateral tubal ligation, hysterectomy or bilateral oophorectomy] or post-menopausal [12 months after last menses] and must use adequate birth control throughout the study period. Adequate birth control is defined as hormonal – oral, implantable, injectable, or transdermal contraceptives; mechanical – spermicide in conjunction with a barrier such as condom or diaphragm; intrauterine device (IUD); or surgical sterilization of partner. For non- sexually active females, abstinence may be regarded as an adequate method of birth control;
  - f) Agree to not participate in another interventional study after providing informed consent and until the study is completed
  - g) Provide written informed consent prior to any study procedure being performed and be able and willing to follow all instructions and attend all study visits
  - h) Be 18-85 years of age at baseline (Visit 2), of either sex and any race or ethnicity

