#### 8.1.4 Procedures for Final Study Entry

Patients who have current DME and overall DME of less than 3 years duration since diagnosis will be approached by the personnel (including but not limited to nurses, optometrists, ophthalmologists) in their clinics. They will be informed about the study by qualified and trained personnel and if willing to participate, they will be asked to read and sign an informed consent form.

Participants will undergo a complete eye examination and fill out a questionnaire on medical and eye health, drug use and allergies.

Patients need to fulfill all inclusion criteria including vision as assessed by ETDRS charts and retinal thickness as assessed by SD-OCT. They must not meet any of the exclusion criteria.

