#### 8.1.5 Methods for Assignment to Treatment Groups:

At visit 2, the subject will be randomized in a 2:1 ratio to active drug or the vehicle group.

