### 8.3 **Examination Procedures**

#### 8.3.1 Procedures to be performed at Each Study Visit with Regard to Study Objective(s)

A complete eye examination will be performed. (Detailed descriptions may be found in an optional study manual if deemed necessary by the sponsor)

- Visual acuity will be measured at every visit using ETDRS chart at 4m with best corrective lenses.
- Intraocular pressure (IOP) will be measured at every visit with Goldmann tonometry or I-CARE tonometry (standardized in each center and the same device to be used for a given patient throughout the study)
- Eye examined at every visit by slitlamp.
- Fundus is examined at every visit through dilated pupils (i.e. using Tropicamide hydrochloride 1% and phenylephrine 2.5%),
- Fundus photographs obtained (optional)
- Optical coherence tomography (SD OCT preferably using Heidelberg Spectralis) performed at each visit to measure central macular thickness (CMT).
- In phakic eyes cataract formation will be graded using the LOCS III system.
- Irritation will be evaluated at every visit by slit lamp biomicroscopy, fluorescein staining when deemed necessary

- Blood pressure should be measured on the patient sitting for at least 2 minutes, on the right arm.
- Quality of life as assessed by NEI VFQ-25 at baseline and 12 weeks.

The full eye examination will be performed before start of the study at screening and then at each visit (Day 1, weeks 2, 4, 8, 12 and 16) until end of the study period.

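### The primary BCVA model omits baseline macular thickness, an entry measurement available on every eligible eye: not an error, but a nearly free gain in precision left unused

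*Combined protocol and SAP*

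**What the plan says.** The primary analysis in section 10.6.3 is a linear model for change in ETDRS letters to Week 12 with "baseline ETDRS BCVA letters as a covariate, and treatment as a main effect factor", on the ITT population with multiple imputation. The supporting analyses in the same section are a two-sample t-test, observed data only, LOCF, BOCF and the per-protocol population. None adds another covariate.

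Baseline CMT is available. Inclusion criterion (a) in section 5.3 requires at least 310 µm "by SD-OCT at baseline (Visit 2) (as measured by the Investigator"), with no upper limit. Section 8.1.4 repeats the requirement: "Patients need to fulfill all inclusion criteria including vision as assessed by ETDRS charts and retinal thickness as assessed by SD-OCT". Section 8.3.1 has OCT "performed at each visit to measure central macular thickness (CMT"), and Appendix 1 schedules it at screening and Day 1.

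On allocation, section 8.1.5 says only: "At visit 2, the subject will be randomized in a 2:1 ratio to active drug or the vehicle group". No stratification factor is described. Section 10.6.2 does not list CMT among the baseline characteristics to be tabulated. Section 3 hypothesises that the drops "improve visual acuity and decrease central macular thickness significantly more than vehicle", so thickness is the second outcome of interest. In section 8.2.2 a rise in CMT is one of the triggers for stopping study drops and allowing rescue.

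**The concern.** Thickness is the other measure of disease severity recorded on every eye at entry. If it predicts BCVA change beyond what baseline BCVA already explains, leaving it out has two consequences. The variation it explains stays in the error term, so the treatment difference is estimated less precisely than the data allow. And a chance difference in thickness between arms is neither prevented by the described randomisation nor corrected in any planned analysis.

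The vehicle arm has only 32 randomised eyes, and the difference needed for success is small, so a shift of half a letter is not trivial. There is also a timing point. An adjustment for CMT is credible if it is fixed before the interim unmasking, but would look selected if added after an imbalance has been seen.

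**Working it through.** **Inputs from the documents.** Section 10.3: a treatment effect of 3.5 letters; an SD of change of 8 letters in both arms; 58 DexNP and 29 vehicle eyes evaluable; 96 randomised (64 and 32, section 5.1). Section 10.4: boundaries z = 1.73051 at half the information and z = 1.08968 at the end. Section 1, baseline CMT SDs in the two earlier DME trials: 164 µm (first trial), 141 µm (second trial, DexNP arm) and 94 µm (second trial, triamcinolone arm).

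**Assumed input.** r, the partial correlation of baseline CMT with Week 12 BCVA change given baseline BCVA. The documents do not give it, so a range of 0 to 0.4 is shown.

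**1. The plan's own figure.** SE of the difference = 8 × √(1/58 + 1/29) = 8 × 0.2274 = 1.819 letters. Standardised effect θ = 3.5/1.819 = 1.924. Power over both looks = 1 − P(Z₁ < 1.73051 − θ√0.5 and Z₂ < 1.08968 − θ), with corr(Z₁, Z₂) = √0.5. This gives 80.6%, so the stated 80% reproduces. The critical difference at the final analysis is 1.08968 × 1.819 = 1.98 letters.

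**2. Precision.** With CMT in the model the residual SD is 8 × √(1 − r²), and step 1 is repeated:

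| r | Residual SD | SE (letters) | Power | Gain (points) | N for the same power, 87 × (1 − r²) |
|---|---|---|---|---|---|
| 0 | 8.000 | 1.819 | 80.56% | 0 | 87.0 |
| 0.1 | 7.960 | 1.810 | 80.83% | 0.3 | 86.1 |
| 0.2 | 7.838 | 1.783 | 81.63% | 1.1 | 83.5 |
| 0.3 | 7.632 | 1.736 | 83.00% | 2.4 | 79.2 |
| 0.4 | 7.332 | 1.668 | 84.99% | 4.4 | 73.1 |

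The table leaves out the cost of the extra term. That cost is a variance factor of about 1 + 1/(87 − 4) = 1.012, which is all that remains if r is near zero.

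**3. How large an imbalance is likely.** At 64 and 32 eyes, SE of the arm difference in mean CMT = SD × √(1/64 + 1/32) = 0.2165 × SD. That is 20.4, 30.5 and 35.5 µm for SDs of 94, 141 and 164 µm. The chance of a difference above 40 µm in either direction is 4.9%, 19.0% and 26.0%.

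**4. What it does to the estimate.** Shift in the BCVA-only estimate = r × 8 × (imbalance/SD). For 40 µm:

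| r | SD 164 | SD 141 | SD 94 |
|---|---|---|---|
| 0.1 | 0.20 | 0.23 | 0.34 |
| 0.2 | 0.39 | 0.45 | 0.68 |
| 0.3 | 0.59 | 0.68 | 1.02 |

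The larger shifts go with the smaller SD, where a 40 µm imbalance is least likely.

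**5. Validity over repeated randomisation.** In simulations of 20,000 trials per scenario (58 and 29 eyes, single look, one-sided 0.15, r = 0, 0.3 and 0.5), mean estimates were about 0 under the null and 3.5 under the alternative, with or without CMT. Type I error was 14.7% to 15.3% throughout. Among null trials in which chance imbalance favoured DexNP by more than one SE, which is about 16% of trials (1 − Φ(1)), the BCVA-only model rejected about 27% of the time at r = 0.3. The CMT-adjusted model rejected about 15% of the time.

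**The case against.** The strongest reply is that nothing in the plan is wrong. The model is pre-specified, adjusts for the baseline of its own outcome, is unbiased over randomisations and keeps its alpha. The sample size uses the SD of unadjusted change, so the stated power never relied on CMT. All of this stands.

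The second reply is that the decisive quantity is missing, and this stands too. Section 3 names two effects of treatment; it does not show that baseline thickness predicts BCVA change. At r of 0.2 or below the gain is about one point of power or less.

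A reader might infer that a thickness imbalance passes straight into the treatment effect, or that the omission biases the trial. The documents do not support either. An imbalance is scaled by the CMT slope, whatever CMT shares linearly with baseline BCVA is already adjusted for, its direction is random, and the planned standard error already includes this variation. Nor can one infer that CMT is left out of the imputation model: section 10.6.3 does not list that model's variables.

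The inputs are also soft. The CMT SDs come from groups of 10 to 19 eyes, and the 310 µm floor may change the spread. OCT devices may differ across about 13 sites, since one device is only preferred, and the entry value is read by the investigator. That could weaken the covariate.

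These points limit the size of the benefit. They do not remove the case for a change that uses data already collected.

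**Conclusion.** The point holds as an improvement in efficiency and robustness, not as an error. The primary model leaves out a pre-treatment severity measure that should be known for every eligible eye, and neither the described randomisation nor any planned analysis deals with a chance imbalance in it.

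The benefit is conditional on r: from nothing (with about 1% variance inflation) near zero to about 4.4 points of power at 0.4. The matching protection against imbalance is about 0.4 to 0.7 letters per 40 µm at r = 0.2, against a critical difference of 1.98 letters. These figures treat 8 letters as the SD left after baseline BCVA is fitted. If baseline BCVA already lowers that SD, the absolute powers change. They also assume that the earlier trials' CMT spread carries over to this population.

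**What to change.** Before the interim unmasking, amend section 10.6.3 so that the primary linear model contains treatment, baseline BCVA and baseline CMT, the last as a second continuous covariate. Define baseline CMT by the rule in section 10.6.1: the last non-missing SD-OCT value before treatment starts. Use the same covariates in the by-visit BCVA models of section 10.6.4, and name baseline CMT among the predictors in the multiple-imputation model. Keep the BCVA-only model as a supportive analysis, and add baseline CMT by arm to the tables in section 10.6.2.

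The cost is a short wording change and one degree of freedom (84 to 83 residual at 87 eyes). No new data, visits or patients are needed. The gain will be smaller if OCT devices differ between sites. If the sponsor prefers not to change the primary model, a pre-specified CMT-adjusted sensitivity analysis is the minimum.

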### 10.2 Hypotheses

The statistical hypotheses for the primary endpoint of mean change from baseline BCVA ETDRS letters in the study eye at Week 12 are as follows:

$H_0$ : The difference between study eyes treated with DexNP and study eyes treated with Vehicle (DexNP – Vehicle) in the mean change from baseline ETDRS BCVA letters to Week 12 (Week 12 – Baseline)  $\leq 0$ .

$H_1$ : The difference between study eyes treated with DexNP and study eyes treated with Vehicle (DexNP – Vehicle) in the mean change from baseline ETDRS BCVA letters to Week 12 (Week 12 – Baseline)  $> 0$ .

The study will be considered a success if  $H_0$  is rejected in favor of  $H_1$  and superiority of DexNP to Vehicle is claimed.

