### **10.5 Study Populations**

*ITT Population:* The intent-to-treat (ITT) population will consist of all randomized subjects, analyzing subjects under the treatment to which they were randomized.

*PP Population:* The per-protocol (PP) population is a subset of the ITT population and includes subjects who do not deviate from the protocol in any way likely to seriously affect the primary outcome of the study, analyzing subjects under the treatment actually received. Important protocol deviations related to study inclusion or exclusion criteria,

conduct of the trial, subject management, or subject assessment will be identified prior to unmasking treatment.

*Safety Population:* The safety population includes all randomized subjects who receive at least one dose of study medication. The safety population will be analyzed as treated and will be used for the safety analyses. No data will be excluded for any reason.

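### The primary success rule has two final thresholds: one-sided p < 0.15 in Section 10.6.3, but 0.13793 (recalculated for actual information) in Section 10.4

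*Combined protocol and SAP*

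**What the plan says.** - Section 10.3 plans the trial for "an overall 1-sided alpha = 0.15", with one interim look at 50% and O'Brien-Fleming alpha spending.
- Section 10.4 gives the levels look by look. At the interim, "the hypotheses will be tested using an efficacy boundary of 1.73051", which is one-sided 0.04177. For the final, "Statistical inference at the final analysis will be made at a 1-sided alpha = 0.13793", with boundary 1.08968. It adds: "Note the actual boundaries will be calculated based on the percent of information used in the interim analyses".
- Section 10.4 also says that "there is no plan to stop early for a claim of superiority" and presents the boundary as protection against that possibility.
- Section 10.6.3 gives the success rule for the primary analysis: "The study will be considered a success and DexNP superior to Vehicle if the one-sided p-value is less than 0.15", together with a difference above zero. It mentions neither the interim nor Section 10.4.
- Section 10.2 ties success to rejecting the null hypothesis, "and superiority of DexNP to Vehicle is claimed", but gives no level.
- Section 10.6.1 and the synopsis set a default of one-sided 0.15 for efficacy tests, which yields where another level is stated.

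**The concern.** Sections 10.4 and 10.6.3 govern one p-value: the final DexNP versus vehicle comparison of change in BCVA at Week 12. A final p of 0.145, for example, meets Section 10.6.3 and fails Section 10.4. Someone would then have to choose the threshold with the p-value already known. The interim makes this more awkward, because a person appointed by the sponsor will see unmasked group summaries.

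A second gap decides whether the looser threshold inflates error. The plan does not say whether crossing the interim boundary rejects the null hypothesis. Section 10.4 tests the hypotheses against that boundary, yet has no plan to stop for superiority. If a crossing counts, spending alpha at the interim and then using the full 0.15 at the end exceeds the overall level in Section 10.3.

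**Working it through.** **Inputs.** Overall one-sided alpha 0.15, 2:1 allocation, difference 3.5 letters, SD 8, 58/29 evaluable and 96 randomized (Section 10.3; the 64/32 split is in Section 5.1). Interim at 50% (44 subjects), with the levels and boundaries of Section 10.4. The success threshold is from Section 10.6.3. All results use the normal approximation.

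**1. Reproduce Section 10.4.** O'Brien-Fleming-type spending at information fraction t is a(t) = 2[1 − Φ(z₀.₉₂₅/√t)].

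- At t = 0.5, a = 0.04177, so c₁ = 1.73051. This matches the plan.
- Solving P(Z₁ > c₁ or Z₂ > c₂) = 0.15 with correlation √0.5 gives c₂ = 1.0897, a nominal 0.1379. This matches to four decimals.
- The plan's own pair of boundaries gives an overall error of 0.1500.

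The Section 10.4 levels are therefore a correct calculation that delivers the overall level in Section 10.3.

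**2. Error and power under each reading at t = 0.5.** One-sided p < 0.15 corresponds to z > 1.0364. With 58/29, SE = 8·√(1/58 + 1/29) = 1.819, and the drift is 3.5/1.819 = 1.924.

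| Interim crossing rejects H₀? | Final level | One-sided error | Power |
|---|---|---|---|
| Yes | 0.13793 | 15.0% | 80.6% |
| Yes | 0.15 | 16.1% | 81.9% |
| No | 0.15 | 15.0% | 81.3% |
| No | 0.13793 | 13.8% | 79.8% |

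**3. How often the two rules disagree, if an interim crossing counts.**

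- Under the null: 0.1611 − 0.1500 = 0.0111, or 1.1% of trials.
- Under the design alternative: 0.8191 − 0.8056 = 0.0135, or about 1.3%.

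**4. Other information fractions.** Because "The intent-to-treat (ITT) population will consist of all randomized subjects" and missing data are imputed, information might be counted as 44/96 rather than 44/87, so I show both.

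| t | Interim level | Correct final level | Error if final p < 0.15 |
|---|---|---|---|
| 0.40 | 0.0228 | 0.1433 | 15.6% |
| 44/96 = 0.458 | 0.0335 | 0.1402 | 15.9% |
| 0.50 | 0.0418 | 0.1379 | 16.1% |
| 44/87 = 0.506 | 0.0430 | 0.1376 | 16.1% |
| 0.60 | 0.0631 | 0.1321 | 16.5% |

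**5. The disputed band in letters** (illustrative: unadjusted, SD 8, t = 0.5).

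- 58/29: 1.0364 × 1.819 = 1.89 to 1.0897 × 1.819 = 1.98.
- 64/32: SE = 8·√(1/64 + 1/32) = 1.732, giving 1.80 to 1.89.

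The planned baseline-adjusted, multiply imputed analysis will have a different standard error.

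**The case against.** **Intent can be recovered.** Section 10.3 calls 0.15 the overall level, Section 10.4 gives look-specific levels, and the default in Section 10.6.1 yields to a level stated elsewhere. A statistician would probably conclude that 0.13793 is meant. That inference is reasonable, but the default does not settle the conflict. Section 10.6.3 is itself a specific success rule, and it applies 0.15 directly to the p-value of the primary analysis. Two specific statements conflict.

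**The inflation is conditional and small.** If the interim can never support a claim, p < 0.15 at the end gives exactly 15.0% and 81.3% power, which is also a coherent design. In the other case the excess at 50% information is 1.1 points on an already lenient level in a Phase IIb trial. Both points stand. However, the plan does not exclude an interim claim, and it lowers the final level as though one were possible. To adopt the alternative, Section 10.4 would have to be rewritten.

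**The rule may be settled elsewhere.** Section 10.6.4 refers to a formal statistical analysis plan for scoring details. Such a document might give the operative level, but the protocol text would still contradict itself.

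**Conclusion.** The contradiction is real, and it concerns the rule by which the trial is declared a success. It should be corrected before any unmasked data are seen. Its numerical effect is modest. At 50% information, overall one-sided error is 16.1% rather than 15.0% if an interim crossing counts and p < 0.15 is used at the end. Over interim timings of 40% to 60% the range is 15.6% to 16.5%. The importance lies in the lack of a unique decision rule, more than in the size of the inflation.

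The Section 10.4 level is the safe resolution, because it holds error at or below 15% whichever way the role of the interim is settled. These figures assume O'Brien-Fleming-type spending, which reproduces the plan's boundaries, and the normal approximation. The power figures also assume the design difference and SD.

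**What to change.** 1. In Section 10.6.3, replace the fixed 0.15 in the success rule with the nominal one-sided final level of Section 10.4: 0.13793 if the interim falls at exactly 50% information, otherwise as recalculated. Keep 0.15 as the overall level, and say in Section 10.6.1 and the synopsis that the primary test follows Section 10.4.
2. In Section 10.4, add one sentence stating that crossing the interim boundary counts as rejecting the null hypothesis. This is secondary to the first change, but it settles what the boundary is for.
3. As a consequence, note in Section 10.6.3 that the 70% interval is descriptive. A final level of 0.13793 corresponds to a two-sided interval of 1 − 2 × 0.13793 = 72.4%, so a 70% interval for the difference could exclude zero when the primary test fails.

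**Cost.** A few lines of text and no extra patients. The final threshold becomes slightly stricter. With the Section 10.4 boundaries at both looks, power is 80.6% with 58/29, so the stated 80% holds (83.1% if all 64/32 contribute). If the sponsor decides that an interim crossing does not count but keeps 0.13793, power with 58/29 is 79.8%.
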